Needs assessment and decision-making tool (NEAT-decision) integrated in clinical practice to enhance patient involvement in Head and Neck Cancer Rehabilitation - a randomised controlled trial

Date: January 31, 2018

Background

The global incidence of Head and Neck Cancer (HNC) is approximately 650,000 per year [1]. Prevalence in the Nordic Countries is 32,500 with an incidence of 4100 annually [2][3][4] and in Denmark there is a prevalence of 8800 with an incidence of 1300 annually [5][6][7]. The five year survival rate is 68% [8].

Head and neck cancer is a heterogenous disease, which involves tumors in the oral cavity, naso-, oro-, and hypopharynx and larynx [9]. More than 90% of malignancies affecting head and neck are squamous cell carcinomas [10]. Risk factors for HNC are primarily linked to lifestyle factors, such as excessive use of tobacco and alcohol [9][10] and HPV-positive oral cancer is linked to sexual behavior [11]. Treatment for HNC is typically surgery, radiotherapy and chemotherapy. One modality or a combination may be used [10]. Treatment at an early stage is most effective, however many patients with head and neck cancers, especially oral cancer, are diagnosed at a late stage [12]. Due to the anatomical sites of the tumors and its treatment, functional abilities can be compromised affecting the patients' psychological and physical wellbeing and social functioning [13][14][15].

The most common complications and sequelae include pain and difficulties with nutrition, voice, swallowing, disfigurement, social life and psychological distress [16][17][18][19][20][21][22]. Artificial nutrition support and an artificial voice [18] may be indicated and the patient may suffer from facial disfigurement due to reconstructive surgery [23].

Patients will experience multiple symptoms occurring concurrently. One symptom may compound another or symptoms may be interrelated affecting quality of life (QoL) more negatively due to the synergistic effect of multiple symptoms [24]. Furthermore interrelatedness exists between the symptom burden, poorer physical functioning, social dysfunction and psychological distress [25]. Patients tend to withdraw from social life, due to disfigurement, problems with speech and eating in public or just interacting with partners, family and friends. Increased social isolation may be a risk factor for poorer physical recovery from the effects of the illness and treatment [26]. Some patients with HNC have a limited social network and/or no partner [27] and lower affiliation to the work force [28] than patients with other cancers, which may intensify the challenges of managing burdensome symptoms. Other factors of influence include lower educational level or low income [29]. Two years after diagnosis, Danish HNC patients are among those with the highest symptom burden, compared to other cancer diagnoses [30]. Finally, HNC is found to be more emotionally traumatic than any other type of cancer [31] and there is a high prevalence of emotional or psychological distress in patients with head and neck cancer, again leading to poorer QoL [32].

Life as it was prior to the disease and treatment cannot be the same afterwards, yet prevention of sequela could give patients better QoL long term. Therefore, there is a need to prevent or alleviate symptoms and the early and late negative effects of the disease and its treatment. Symptoms that could lead to sequela need to be assessed and managed early by referral to specialist follow-up i.e. speech-language pathologist, physio-and occupational therapists, dietician, clinical nurse specialist and psychologist [33][34][35]. To a greater extent, patients with HNC come from backgrounds of short education and manual labour, which place them at risk for health disparity [36][37][38]. The type and quality of decision-making tools used to assess health and rehabilitation needs are important to consider in patients with low health literacy [39]. Acknowledgment of the importance of patient-involvement in needs assessments using Patient Reported Outcomes (PRO) is growing. However present PRO questionnaires have certain limitations. Firstly, they have been developed for research purposes, therefore little is known about how these can be applied in the clinical setting to obtain the patient's information on the symptoms experienced [40]. Secondly, PRO questionnaires do not incorporate needs assessments [40]. Finally, there is currently, a lack of knowledge

regarding which type of decision making assessment tool would be optimal in patients with short education and low health literacy.

Study hypothesis and objective

The study's *hypothesis* is that a disease-specific patient-reported needs assessment tool integrated in the clinical management of HNC will increase patient involvement in decision making, control the short and long term symptom burden and improve short and long term health related quality of life (HRQoL) in HNC patients, primarily surgically treated. The *purpose* of the study is to investigate whether a systematic patient reported needs and concerns assessment integrated prior to and during consultations with health care professionals (HCP), is feasible and safe, and will improve patient involvement in decision making during the consultation. Further, whether patient involvement will result in increased referral to the multi-disciplinary team and ultimately reduce the symptom burden, improve physical, mental and social wellbeing and global HRQoL.

Study designs and methods

Study *one* is a literature review exploring early and late physical and psychosocial effects of surgery. Study *two* is designed as a qualitative study exploring nurse-patient interactions during formal and systematic rehabilitation consultations. Study *three* is a randomized, controlled trial (RCT) on the effect of applying a disease-specific needs and concerns assessment instrument in the context of clinical nurse consultations assessing and managing the patient's rehabilitation needs. Prior to the RCT, a cross-cultural validation of the instrument Patient Concerns Inventory (PCI) will be carried out. The PCI was developed at Aintree University Hospital, Liverpool, Great Britain, specifically for HNC patients[41] and since the PCI functions with a touch screen solution, an IT solution will be developed. The randomized controlled study will include a control group (CG) and intervention group (IG) and take place at the Department of Otolaryngology, Head and Neck Surgery and Audiology, (Dept. ORL, H&N), Copenhagen University Hospital, Rigshospitalet.

Study one – Literature Review

Aim

To conduct a literature review to explore the early and late physical and psychosocial effects of patients primarily surgically treated for oral cancers and to investigate the factors that influence these effects.

Material and methods

Perform a systematic literature search in PubMed, Cinahl and PsycInfo, using the Boolean search operators and the search words: mouth neoplasms, rehabilitation, oral surgery, anxiety, body image, depression, distress, dysphagia, eating, pain, psychosocial, speech and swallowing. Include English language quantitative and qualitative articles published between January 2004 and January 2014 that investigates physical and psychosocial wellbeing in patients primarily surgically treated for oral cancer (non HPV-induced squamous cell carcinomas) at one or more time points along the treatment trajectory, including time of diagnosis. Exclude articles that includes samples of patients with diagnoses other than non-HPV induced squamous cell cancer of the oral cavity and/or only treated oncologically, as well as articles describing surgical procedures.

Methodological and statistical quality of the included studies will be assessed independently by two persons using a 7-item criteria checklist [42]. The number of articles accessed, screened and read, will be noted, as well as time of measurements; types of articles (quantitative or qualitative articles) and study

designs. Finally the key areas of the physical and psychosocial early and late effects of the surgical treatment for oral cancers and the factors that influence these effects will be summarised.

The literature review has been published ([name]; [name]. "Early and late physical and psychosocial effects of primary surgery in patients with oral and oropharyngeal cancers: a systematic review," *Oral Surg. Oral Med. Oral Pathol. Oral Radiol.*, vol. 121, no. 6, pp. 583–594, 2016).

Study two – Qualitative study

Aim

To explore the nurse-patient interaction, patient involvement and communication practices during nurse consultations in post-surgical patients with head and neck cancer.

Methods and procedures

An exploratory and descriptive qualitative study informed by ethnographic fieldwork. The study will include nonparticipant observations during nurse consultations, individual patient interviews and focus group interviews with nurses performing nurse consultations, employing Interpretive Description [43][44].

Population and recruitment

Included are patients, who have been diagnosed and treated surgically for head and neck cancer, at stage T3 or T4, and able to speak and understand Danish. Excluded are patients treated surgically for thyroid or parotid cancers, patients referred to adjuvant radio – or chemotherapy and patients with unstable psychiatric illness.

Patients (n=15) will be informed about observational studies through posters in Dept. ORL, H&N on the observation days during June – July 2017 and January 2018. Using purposive sampling, patients (n=15) will be recruited for individual interviews after surgery for Head and Neck Cancer, from Dept. ORL, H&N, at the following three time points: before discharge, seven – ten days post-op and two months post-op in the period from December 2017 – February 2018. Nurses (n=4) who deliver nurse consultations will be recruited for a focus group interview at the Dept. ORL, H&N, through individual contact during February 2018.

Data analysis

The focus group interview and the individual interviews will be recorded digitally, transcribed verbatim and coded in the software program NVivo. Thematic analysis will follow a model where the transcriptions will be read and re-read, coded according to emerging themes, a clustering of themes and finally reaching a number of themes, which describes the patient's and nurses experiences with nurse-patient interactions [45]. Observations will be recorded as short field notes during observations and following this expanded as notes in a text-file. The field notes will follow the same analytic process as the interviews. Researcher triangulation will be applied.

A detailed project description for this part of the study is attached (Appendix I)

Study three – Randomized controlled trial

Aim

To evaluate the safety and effect of the PCI integrated in clinical practice. Specifically, to investigate whether patients and Health Care Professionals (HCP) find the PCI applicable and useful in assessing and managing care and rehabilitation needs. Furthermore, whether patients are referred more often to multi-disciplinary follow-up, which types of follow-up and whether the new needs assessment and decision-

making tool improves the interaction between HCPs and patients. Lastly, to explore whether patients experience a reduced symptom burden and improved HRQoL.

Linguistic and cross cultural validation of the PCI and Development of an IT-solution

Prior to the RCT, a linguistic and cross cultural validation of the PCI and development of an IT-solution within the context of a head and neck department in Denmark will be carried out. The PCI is a 57 item solution, where patients can select a range of items related to functional, emotional, social and existential areas [46] using touch screen buttons, which allows the patients to choose the items, they wish to discuss with the HCP. This enables the patient to express their concerns and symptoms and choose those items, they find important and meaningful to discuss. The PCI includes a brief electronic version of the University of Washington Quality of Life Questionnaire (UW-QoL), which aids the HCP in addressing needs that the patient may not be attentive to [41].

The IT-solution functions with 'buttons' on a touch-screen. Each 'button' corresponds to one item. Thus the solution makes it easy to attain an overview of the items [41]. The solution has been approved by Center for IT, Medico and Telephone (CIMT) of the Capital Region, who requires that the actual programming is done by a private company (I-r software a/s). A four step validation process will follow the EORTC-guidelines for cross-cultural adaptation of QoL questionnaires [47] and include *linguistic and cultural validation*, but not psychometric, as the PCI is not a QoL questionnaire: (1) forward and (2) backward translation, (3) pilot testing a paper version by HNC patients (n=10) and patients from patient networks (Dansk Landsforening for Hals- og Mundhuleopererede and Netværk for hals og mundhulekræft). The testing will include interviews based on a brief structured questionnaire on the understand ability of the PCI [47]. (4) Finally, to ensure IT-solution suitability in clinical practice, it will be pilot tested by HNC patients (n=10), who will be interviewed on the basis of a brief questionnaire on the applicability and usefulness of the touch-screen solution. An in-depth validation protocol is attached (Appendix II). Two native Danish and English speaking persons will be asked to carry out the forward and backward translation. Patient recruitment for step 4 (n=10) and 5 (n=10) of the validation process will be identical. The inclusion and exclusion criteria are the same as in study two. The PCI and IT-solution will be tested and re-tested on new patients until problems with comprehensiveness is resolved. A final translation report will be sent to consultants at Aintree Hospital, Liverpool for approval.

Design and methods (Figure 1 attached)

The study is designed as a two arm randomized controlled study with a control group (CG) and intervention group (IG). Patients will be randomized via Research Electronic Data Capture (REDCap), an electronically based system for keeping research data, containing a randomisation module. Patients will be randomly assigned 1:1 to either CG or IG, stratified according to newly diagnosed and recurrences. The assignments will not be blinded to either investigator or patients.

Population and recruitment

Total study population (n=128). CG (n=64) and IG (n=64) will be recruited consecutively during hospital admission post-surgery from April 2018 - March 2019. The inclusion and exclusion criteria will be the same as in study two.

Statistics

The sample size of this study (n=128) is based on a power calculation with an SD of 20; effect size 10 and power of 0,8. SD is based on similar studies on Head and Neck patients [48] and effect size on recommendations from EORTC [49], further the sample size is based on previous research in the Department of ORL H&N, Copenhagen University Hospital. To account for an expected dropout rate and non-recruitment rate of approximately 20% [50][51], the number of patients included in the study will be 160. Furthermore, based on the ratio between newly diagnosed patients and recurrences, we will stratify each study arm as follows; newly diagnosed (n=43) and recurrences (n=21).

Procedures

CG will receive standard care according to the Danish Health and Medicine Board's follow-up programme for HNC patients [52], which requires all patients have their physical, emotional, social and existential needs assessed by interview with a HCP, at three time-points post-treatment. At present this is done at the Dept. of ORL, H&N during the admission period post-surgery, two weeks and two months post-surgery, by a staff nurse who is a member of the rehabilitation team who perform nurse consultations. These consultations take place after the appointment with the surgeon. The nurse refers the patient to physical rehabilitation if needed.

IG will receive the PCI intervention integrated in clinical practice in accordance with present requirements as stated by the Danish Health and Medicine Board follow-up program for HNC patients [52]. The main investigator (AM) or the research assistant (a nurse from the rehabilitation team), will carry out the nurse consultation in 6 steps: 1. Welcoming the patient; 2. Introducing the patient to the PCI and guide in the use of this; 3. Starting with the symptoms and concerns the patient has highlighted in the PCI, the consultation will be based on these; 4. Follow up on the patients symptoms, concerns and emotional reactions or problems from a professional point of view; 5. Accompany and support the patient during the appointment with the surgeon and in cooperation with the patient and the surgeon ensure that problems arising from the nurse consultation needing medical attention are focused on; 6. Continue the consultation after the appointment with the surgeon; refer the patient to multi-disciplinary team members when needed. The nurse consultations will take place during the admission period post-surgery, two weeks and two months post-surgery. The management of symptoms arising from the needs assessment using the PCI, will be based on an evidence-based manual prepared for this purpose. In preparation of the intervention, the HCP multidisciplinary staff will be introduced to the intervention, including the use of the PCI, through written and oral information. The research assistant will be formally trained in the use of the PCI and interviewing patients with physical and emotional needs.

Outcome measures

Quantitative outcomes: The primary outcome will measure the effect of the intervention by PRO quality of life and symptom questionnaire EORTC QLQ-H&N35. H&N35 is a 35-item questionnaire to be used with a core questionnaire[53]. The H&N module particularly measures oral pain, nutritional and voice problems. Patients will be asked to complete the EORTC QLQ-H&N35 at four time-points, 1) baseline (before randomisation) 2) between discharge and first follow-up in OPD 3) 7 days after first and 4) second post-surgical appointments – by telephone. Presence and severity of symptoms will be evaluated by MDASI-HN (MD Anderson Symptom Inventory) which is a multi-symptom patient-reported outcome measure for clinical and research use ([54]). MDASI-HN is a 28-item questionnaire which measures symptoms of HNC patients. Finally the patients physical activity level will be measured according to the Saltin-Grimby Physical Activity Level Scale, which

is a four-item questionnaire measuring the patients activity level [55]. MDASI-HN and Saltins will be used at four time-points – baseline (before randomization); before discharge; at first and second post-surgical appointment. Demographic and medical data (age, sex, diagnosis) will be registered at baseline and the types and number of multi-disciplinary referrals will be registered at each follow-up. The outcomes and items patients choose on the PCI will be registered. Finally the acceptance and adherence to the study will be assessed by registering the number of patients recruited and participating in the study and the attrition rate.

Qualitative outcomes: Qualitative interviews and focus group interviews will be carried out at the second post-surgical appointment to explore patient and HCP perspectives regarding the use of PCI. The interviews will be based on semi-structured interview guides. For the qualitative individual interviews, patients from IG (n= 15) will be recruited at the OPD, at the two-week appointment, from August to September 2018 and carried out October to November 2018. For the focus group interview, doctors and nurses (n=6-8) will be recruited at the Department from January - February 2019 and carried out March 2019.

Data and analysis

The baseline demographic, medical data and number and types of referrals to multi-disciplinary team will be compared between the two trial arms using the chi-square test for categorical variables, the Student's t-test for normally distributed continuous variables, and the Mann-Whitney test for non-parametric variables. Descriptive data will be presented as means with standard deviations, medians with inter-quartile ranges or frequencies with percentage depending on the distribution of the variable. For the intervention group; feasibility, acceptance, adherence, attrition (and reasons) and safety will be calculated in mean and percentage. Data from the PRO questionnaires will be keyed in a database, compared across groups using SAS program to evaluate for statistical difference and effect size, by two-sample t-test. Analysis of covariance (ANCOVA) will be applied for comparisons of groups adjusted for, e.g. smoking and alcohol consumption status or sex.

Qualitative: The focus group interview and the individual interviews will be recorded digitally, transcribed verbatim and coded in the software program NVivo. Thematic analysis will follow a model where the transcriptions will be read and re-read, coded according to emerging themes, a clustering of themes and finally reaching a number of themes, which describes the patient's or HCP's experiences with the PCI in the new model of care [45]. Researcher triangulation will be applied.

A detailed project description for this part of the study will be developed.

Ethical considerations

Patients will receive oral and written information that participation is voluntary and that they may withdraw at any time without affecting treatment and care. Written informed consent will be obtained from patients participating at time of recruitment. The Regional Ethics Committee of the Capitol Region of Denmark has been approached regarding approval of the study. They have assessed this and deemed an approval unnecessary (Jr. no: 16036032)

The study has been approved by the Danish Data Protection Agency (RH-2017-264 ,I-Suite no: 05781) and will be sought registered at ClinicalTrials.com. The study will be carried out in accordance to the Helsinki Declaration and published according to Vancouver guidelines.

Clinical Perspectives

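### Global HRQoL is part of the stated purpose, but no core questionnaire or other measure described as global HRQoL is named or scheduled for both arms

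*Protocol*

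**What the plan says.** The section Study hypothesis and objective lists several things that the intervention might achieve. The last of them is to "ultimately reduce the symptom burden, improve physical, mental and social wellbeing and global HRQoL". Symptom burden and global HRQoL appear there as separate items. The Aim of Study three (the randomised trial) is more modest: lastly, "to explore whether patients experience a reduced symptom burden and improved HRQoL", without the word *global*.

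Under Outcome measures, "The primary outcome will measure the effect of the intervention by PRO quality of life and symptom questionnaire EORTC QLQ-H&N35". The same paragraph adds that "H&N35 is a 35-item questionnaire to be used with a core questionnaire" and that "The H&N module particularly measures oral pain, nutritional and voice problems". The scheduling sentence reads "Patients will be asked to complete the EORTC QLQ-H&N35 at four time-points" and mentions no companion instrument. Two further patient-reported instruments follow. One is the MDASI-HN ("MDASI-HN is a 28-item questionnaire which measures symptoms of HNC patients"); the other is the Saltin-Grimby scale of physical activity.

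One more quality-of-life tool is mentioned. The section on validating the PCI says that it contains a short electronic UW-QoL, there to help the clinician pick up needs the patient may overlook. Under Procedures, the PCI is given to the intervention group, while controls have their needs assessed by interview as in standard care.

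**The concern.** The protocol says that its primary instrument accompanies a core questionnaire, and then schedules the instrument without one. The purpose names a construct, global HRQoL, that no scheduled instrument is described as measuring. The UW-QoL cannot fill the gap, because one arm never sees it.

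If the schedule is carried out literally, the trial ends with no between-arm estimate of global HRQoL. A difference on head-and-neck scales could then be reported under a purpose that speaks of global HRQoL. The choice and timing of questionnaires are fixed in this protocol, so an analysis plan that is not at hand cannot repair the gap: it can only analyse what was collected. Baseline is taken before randomisation, so a baseline score that is missed cannot be obtained later.

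**Working it through.** The point concerns what is collected, so the check sets every quality-of-life, symptom or activity instrument in the protocol against the purpose.

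| Instrument | How the protocol describes it | Arms | Scheduled times | Described as global HRQoL? |
|---|---|---|---|---|
| QLQ-H&N35 | quality-of-life and symptom questionnaire, with emphasis on oral pain, nutrition and voice | both | four: baseline; between discharge and first outpatient follow-up; by telephone 7 days after each of the two post-surgical appointments | no |
| MDASI-HN | presence and severity of symptoms, 28 items | both | four: baseline; before discharge; first and second post-surgical appointments | no |
| Saltin-Grimby | physical activity level, four items | both | as MDASI-HN | no |
| Core questionnaire | unnamed companion of the H&N35 | not stated | none stated | not described |
| Brief UW-QoL | aid to the clinician, inside the PCI | intervention only | with the PCI | no |

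**Step 1: what a between-arm comparison needs.** The estimate is (mean in the intervention group) minus (mean in the control group) on the same instrument at the same time. Three instruments meet that condition, and none is described as a global HRQoL measure.

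**Step 2: can the UW-QoL serve?** Outcome measures says that PCI outcomes and chosen items will be registered, so UW-QoL answers might be stored. They would exist for the intervention group only, so the control term is missing. The qualitative interviews cannot help either, since they recruit intervention patients and staff.

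**Step 3: is the core questionnaire mentioned elsewhere?** The Core 30 appears only in the title of reference [49], which the Statistics section cites for its effect size. It is not listed as an outcome.

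**Step 4: does a repair disturb the sample size?** Inputs from the Statistics section are SD 20, difference 10 and power 0.8. Allocation is 1:1 (Design and methods). The significance level is not stated; two-sided 0.05 is assumed.

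- Normal approximation: n per arm = 2 × (1.96 + 0.8416)² × (20/10)² = 2 × 7.849 × 4 = 62.8, so 63 per arm and 126 in total.
- Exact two-sample t-test: 63.77, so 64 per arm and 128 in total, which is the protocol's figure. Power at 64 per arm is 0.801.
- Allowance for 20% loss: 128 / 0.8 = 160, also the protocol's figure.

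The calculation reproduces. Adding a questionnaire for a non-primary objective leaves it unchanged.

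**The case against.** The strongest reply is that the core questionnaire was meant all along. Saying that the module goes with a core can be read as giving the core wherever the module is given, and the effect size rests on a guideline for the Core 30. In addition, Figure 1, which is attached to the design section, is not shown, and Data and analysis promises a further detailed project description, though possibly only for the qualitative part. This stands in part. A reader might infer that global HRQoL will never be measured, but that would turn silence into a definite fact. The documents support only the narrower statement that nothing is named or scheduled. The text still needs changing, because staff working from Outcome measures would not know to hand out a core questionnaire, or when.

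A second reply is that the objective is soft. The purpose is to investigate, it covers all three studies, and the trial's own aim is to explore improved HRQoL without the word *global*. The H&N35, which the protocol calls a quality-of-life questionnaire, serves that aim in both arms. This also stands, and it confines the mismatch to global HRQoL in the purpose.

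A third concerns mental and social wellbeing. A reader might conclude that these go unmeasured too, so that a benefit on distress would be missed. The documents do not support that. They do not list the scales of the H&N35 or the MDASI-HN, and the H&N35 is said to measure oral pain, nutrition and voice *particularly*, not exclusively. Physical aspects are at least partly covered by the activity scale and the symptom items.

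**Conclusion.** The point holds for global HRQoL. The purpose names it and the protocol says that its primary instrument has a core companion, yet none of the four H&N35 time-points carries a named core questionnaire or another measure described as global HRQoL for both arms. Disease-specific quality of life, symptoms and activity level can be compared between arms as planned.

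This rests on the visible text, on taking the protocol's own descriptions of its instruments at face value, and on the material not shown not containing a fuller schedule. It is worth correcting before recruitment starts. It does not threaten the primary comparison or the sample size.

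**What to change.** In Outcome measures, name the EORTC core questionnaire (the Core 30, which reference [49] already concerns). Schedule it in both arms at the four H&N35 time-points, including baseline before randomisation, and state that it is the measure for the global HRQoL objective. The documents do not describe its scales, so the sponsor should also name the score to be used. The cost is a modest extra questionnaire burden at contacts that already take place, two of them by telephone, with no added visit and no change to 128 or 160.

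If it will not be collected, remove *global* from the HRQoL wording in Study hypothesis and objective, and limit the trial's conclusion to disease-specific quality of life and symptoms. That is a wording change only; its price is giving up the global claim.

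### The protocol gives two trial sizes, 128 to be recruited and 160 to be included, and its per-arm stratum numbers fit only 128, so the number to randomise is not fixed.

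*Protocol*

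**What the plan says.** All the statements are in Study three of the protocol.

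- **Design and methods:** "Patients will be randomly assigned 1:1 to either CG or IG, stratified according to newly diagnosed and recurrences".
- **Population and recruitment:** "Total study population (n=128). CG (n=64) and IG (n=64) will be recruited consecutively during hospital admission post-surgery".
- **Statistics, basis:** "The sample size of this study (n=128) is based on a power calculation with an SD of 20; effect size 10 and power of 0,8".
- **Statistics, allowance:** "To account for an expected dropout rate and non-recruitment rate of approximately 20" per cent, "the number of patients included in the study will be 160".
- **Statistics, strata:** in the next sentence, "we will stratify each study arm as follows; newly diagnosed (n=43) and recurrences (n=21").
- **Outcome measures:** acceptance and adherence are to be assessed by "registering the number of patients recruited and participating in the study and the attrition rate".

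The visible text does not give 80 per arm, does not call 128 the number to be analysed, and does not state a number to randomise in so many words. Figure 1, which the Design and methods heading cites, is not shown in the text available for review.

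**The concern.** Being recruited and being included both describe patients entering the trial, yet the protocol attaches 128 to one and 160 to the other. The stratum numbers come straight after the 160 but belong to a trial of 128. Two of the three operational statements therefore point to 64 per arm and one to 80.

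The allowance adds to the doubt because it puts dropout and non-recruitment into one rate. Patients who decline are lost before randomisation and do not thin the randomised arms. Only loss after randomisation reduces the analysed share. Without the split, a reader cannot tell whether 160 counts patients randomised or patients approached.

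What is at stake is the stated power. A team that follows the recruitment sentence and the strata would close at 64 per arm, the exact requirement with nothing in reserve. A team that follows the allowance sentence would continue to 80 per arm. The choice has to be settled before recruitment ends, because it cannot be repaired at the analysis stage.

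**Working it through.** **Inputs.** Difference 10, SD 20 and power 0.8 (Statistics); two-sample t-test (Data and analysis); 1:1 allocation (Design and methods); combined loss of about 20% (Statistics). The significance level is not stated, so two-sided 0.05 is assumed. One-sided 0.05 would need only about 50 per arm and does not match the protocol's figure.

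**1. Reproducing 128.** The standardised difference is d = 10/20 = 0.5. The normal approximation gives n per arm = 2 × (1.96 + 0.84)² × 20²/10² ≈ 62.8, rounded up to 63 (126 in total). The exact t-test gives 63.77, rounded up to 64 per arm, so 128 in total. The stated figure is reproduced, and it is the number needed **in the analysis**.

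**2. Reproducing 160.** 128/(1 − 0.20) = 160, and back again 160 × 0.8 = 128. This inflation is also correct.

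**3. Checking the strata.** 43 + 21 = 64 per arm, and 2 × 64 = 128. A randomised total of 160 means 160/2 = 80 per arm. At the same ratio that is 80 × 43/64 = 53.75 newly diagnosed and 80 × 21/64 = 26.25 recurrent, about 54 and 26.

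**4. Power under each reading** (t-test, d = 0.5, two-sided 0.05):

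| Randomised per arm | Loss after randomisation | Analysed per arm | Power |
|---|---|---|---|
| 64 | 0% | 64 | 0.80 |
| 64 | 5% | 61 | 0.78 |
| 64 | 10% | 58 | 0.76 |
| 64 | 15% | 54 | 0.73 |
| 64 | 20% | 51 | 0.71 |
| 80 | 10% | 72 | 0.85 |
| 80 | 20% | 64 | 0.80 |

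The 51 per arm comes from 128 × 0.8 = 102.4 patients. It is the worst case, in which the whole pooled 20% falls after randomisation.

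**5. Effect of the pooled 20%.** If all of it is dropout, 160 are randomised and 128 analysed. If all of it is non-recruitment, 160 are approached, 128 are randomised and nothing is left for dropout. Mixed splits fall between these. The text therefore allows any randomised total from 128 to 160, a spread of 160 − 128 = 32 patients.

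**The case against.** The strongest reply is that nothing has been miscalculated. The Statistics paragraph derives 128 from the power calculation and then says that the intake is raised to 160 to cover losses. A statistician would naturally read 128 as the requirement and 160 as the inflated intake, with the 43/21 split simply describing the powered 64 per arm. To stop at 64 per arm, a team would have to ignore an explicit sentence. Figure 1 may also label the numbers.

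Much of this stands. Both totals are arithmetically right, so this is an inconsistency between statements and not a wrong sum. 160 randomised with 128 analysable is the likely intent. The 0.71 needs several unfavourable conditions at once, and at 5% to 10% loss the shortfall is modest (0.78 to 0.76).

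It does not remove the contradiction. The recruitment sentence attaches 128 to patients being recruited, and the arms are sized at 64 immediately after the 160 is given. A further reading, with 160 approached and about 128 randomised, fits the recruitment sentence and the strata, though it fits the word used for the 160 poorly. That a third reading is possible shows that the number to randomise is open. Even if Figure 1 gives a single number, these two paragraphs would still have to be brought into line with it.

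The separate registration of recruitment and attrition under Outcome measures is only minor support. It shows that the protocol can tell the two quantities apart, but it does not contradict a pooled planning rate.

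**Conclusion.** The concern holds. The protocol states two sizes for the same trial, 32 patients apart, and its stratum numbers match only the smaller one. Under the protocol's own 20% allowance, randomising 160 keeps the stated power of 0.8 even if all the loss comes after randomisation. Randomising 128 falls below it with any loss after randomisation, reaching 0.71 in the worst case. The power figures assume two-sided 0.05 and the two-sample t-test. The contradiction itself depends on neither.

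**What to change.** State one randomised total and use it throughout Population and recruitment, Statistics and Figure 1.

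- **If 160 is intended:** write 160 randomised (80 per arm) and 128 expected to be analysable. Give about 54 newly diagnosed and 26 recurrent per arm, as expectations and not quotas. Say how much of the 20% is dropout after randomisation.
- **If 128 is intended:** remove the 160, or relabel it as the number approached if that is what it means. Restate the power for the loss expected after randomisation, for example 0.76 at 10% and 0.71 at 20%.

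The significance level and sidedness behind the calculation should be written in the same sentence.

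The cost is wording only. The first option needs no patients beyond the 160 already stated. The second costs a lower stated power.
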